### **3.2.2 Study Intervention Phase**

Randomization will occur after eligibility is confirmed AND the baseline stool sample is received at the University of Pennsylvania.

To determine the participant's randomization, the Site Coordinator must first confirm receipt of the stool sample at Penn and then confirm the participant's eligibility based on Visit 1 data collection and document both in the Data Management System (DMS). Upon documentation of both in the DMS, the DMS will automatically provide the Site Coordinator with the participant's assigned diet.

The Site Coordinator will inform the participant of their assigned diet in person or over the phone.

Participants will be provided instructions about how and when they will receive their study diet meals and will be assisted with registering with the vendor that provides the study diet meals. Participants will follow the study diet for 6 – 12 weeks. The first 6 weeks the food will be provided from the study meal vendor. The second 6 weeks the participant will be responsible for following the study diet on their own.

### **3.2.3 Follow-Up Phase**

Participants will receive daily online surveys to complete for up to 16 weeks starting after consent. During weeks 1-6 participants will receive all of their meals shipped directly from the food vendor to the participant. At week 3 participants will receive an online survey via email or text about their satisfaction with the study diet. On Day 42 (+ or – 3 days) participants will come into the clinic for a visit that will involve: collection of information about their symptoms which will be used to obtain an sCDAI score, a physical exam to obtain CDAI score, one tube of blood drawn to measure hsCRP and one for HCT, possibly a third tube of blood drawn for plasma (for applicable sites only), providing information about adverse events, medications, joint symptoms, providing health status information (physical, mental and social) to obtain a PROMIS score, and being weighed. They will take a satisfaction survey about the study diet. They will collect one stool sample during days 38-40 and will ship it to [name] laboratory at the University of Pennsylvania. On a randomly selected day during week 6, participants will be interviewed by a dietitian over the phone who will ask them about what they ate on the previous day.

During weeks 7-12, participants will no longer receive prepared meals, but will adhere to their study diet on their own. Participants will be given recipes and instructions about how to prepare study diet meals on their own. Participants will also receive an online survey about their satisfaction with the study diet during week 9.

On Day 84 (+ or – 3 days), participants will come into the clinic for a visit that will involve: collection of information about their symptoms which will be used to obtain an sCDAI score, a physical exam to obtain CDAI score, one tube of blood drawn to measure hsCRP and one for HCT, providing information about adverse events, medications, joint symptoms, providing health status information (physical, mental and social) to obtain a PROMIS score and being weighed. Participants will take a satisfaction survey about the study diet online and they will complete a Diet History Questionnaire online.. The participant will collect one stool sample during days 80-82 and ship it to [name] lab at the University of Pennsylvania. On a randomly selected day during week 12, a dietitian will contact participants by phone to ask them about what they ate on the previous day. Participants complete the study at the end of the week 12 visit.

Site Coordinators may call participants as needed to remind them of their upcoming study visits, sample collections, and online surveys.

### **3.3 Allocation to Interventional Group**

Participants who meet all eligibility requirements, provide a baseline stool sample, and complete 5 to 7 days of sCDAI online surveys, will be randomly assigned to one of the study diets in a 1:1 ratio of SCD:MSD. The randomization will be stratified based on whether the participant is currently using a biologic therapy for CD. As such, there will be two strata as follows:

Biologic Therapy
Yes
No

Randomization will be blocked using variable block sizes ranging from 2 to 4. A study biostatistician at the DCC will generate the randomization scheme which will be incorporated into the study data management system. Once the randomization form is completed in the data management system it will generate the participants' study diet assignment.

### **3.4 Study Endpoints**

#### **3.4.1 Primary Study Endpoints**

##### **3.4.1.1 Symptomatic remission**

Symptomatic remission will be assessed at 6 weeks. This is defined by patient reported outcomes (PROs) focusing on the cardinal symptoms of CD - diarrhea, abdominal pain, and general wellbeing. These have been combined into the Short Crohn's Disease Activity Index (sCDAI) which provides a composite measure of the PROs. Symptomatic remission will be defined as a sCDAI <150^74 in the absence of the need for increasing corticosteroid dose or initiation of new therapies for CD during the study period. Participants who withdraw from the study prior to week 6 will be categorized as failing to achieve symptomatic remission and other related outcomes.

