#### **4.2 Exclusion Criteria**

1. Pregnancy
2. sCDAI >400
3. Hospitalized patients
4. Anticipated need for surgery within 6 weeks of randomization
5. Use of the Specific Carbohydrate Diet within 4 weeks of screening
6. Start or change\*\*\* dose of thiopurines (azathioprine and 6-MP), methotrexate, natalizumab, or vedolizumab within 12 weeks prior to screening
7. Start or change\*\*\* dose of anti-TNF agents (including infliximab (Remicade), adalimumab (Humira), certolizumab pegol (Cimzia), golimumab (Simponi) or ustekinumab within 8 weeks prior to screening.
8. Start or change in dose of any 5-ASA medications within 2 weeks of screening.
9. Start or change dose of corticosteroids within 1 week of screening or a dose >20mg/day prednisone or equivalent\*
10. Use of antibiotics (other than topical formulations) for any reason within 2 weeks prior to screening
11. Known symptomatic intestinal stricture.
12. Presence of an ostomy
13. Baseline stool frequency >4 bowel movements/day when well

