## **6.5 Subject Withdrawal**

Participants may withdraw from the study at any time.

Participants may be withdrawn at the discretion of the investigator prior to randomization for the following reasons:

- Failure to provide the baseline stool sample
- Failure to complete at least 5 of the 7 baseline sCDAI surveys

Participants will be withdrawn from the study if they experience worsening symptoms requiring a change in their Crohn's disease treatment, the initiation of an antibiotic for gastrointestinal symptoms, and/or an increase of greater than 10mg/day of prednisone or equivalent for a non-gastrointestinal condition\*.

*\*Please see section 6.2.2 for equivalency chart*

Participants who have been randomized to one of the two diets and withdraw early from the study should complete an end of study visit and provide a stool sample at the time of withdrawal as described in section 6.2.5.

If the participant wishes to discontinue the study diet early for reasons not related to worsening Crohn's Disease (e.g., they don't like the diet), they will be asked to remain in follow-up and complete the next in-person visit at the target date of that visit (either week 6 or week 12). This will be the end of study visit.

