The primary outcome will be measured at 6 weeks. The 6 week study duration was selected for the following reasons:

- a. Our stakeholders informed us that they would be unlikely to continue trying a dietary therapy if they did not observe a benefit within 6 weeks.
- b. In Breaking the Vicious Cycle, it is stated that one month is sufficient to know if the SCD is working.
- c. The practical implications of not allowing changes to the medical therapy for patients with active CD for much longer than 6 weeks could be a major disincentive to enrollment.

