### **9.2.3 Expected Adverse Events**

As a short term study of two diets, there are few expected risks of the two interventions. These include allergic reaction to a component of the food, intolerance of the food other than as an allergic reaction, and worsening of Crohn's disease manifested as any of the following: worsened abdominal pain, worsened diarrhea, bowel obstruction, penetrating complications such as fistula or abscess. In addition, worsening of extraintestinal manifestations of Crohn's disease is possible, such as worsening arthropathy, mouth sores, skin rashes including pyoderma gangrenosum and erythema nodosum, and ocular manifestations such as episcleritis or uveitis. The Crohn's disease related adverse events would not be considered to be caused by the diets, but rather as a consequence of failure of the diet based therapy to induce disease remission. Some exacerbations of Crohn's Disease may result in hospitalization and/or the need for surgery. In rare circumstances, exacerbations of Crohn's disease may be life-threatening.

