#### **5.5.1. Outcome definitions**

Clinical remission will be defined use the sCDAI which provides a composite measure of relevant patient reported outcomes (PROs). Symptomatic remission will be defined as a sCDAI <150^4 in the absence of the need for increasing corticosteroid dose or initiation of new therapies for CD during the study period. Participants who withdraw from the study prior to week 6 will be categorized as failing to achieve symptomatic remission and other related outcomes.

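### Raising the dose or frequency of a non-steroid Crohn's drug already in use, without worsening symptoms, does not void remission, so a drug effect can be scored as remission on the diet

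*Combined protocol and SAP*

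**What the plan says.** - **Endpoint.** Protocol 3.4.1.1 and 8.1 set symptomatic remission at a week 6 sCDAI below 150, "in the absence of the need for increasing corticosteroid dose or initiation of new therapies for CD during the study period". SAP 5.5.1 repeats it: "Symptomatic remission will be defined as a sCDAI <150", again subject to no "need for increasing corticosteroid dose or initiation of new therapies for CD during the study period". CDAI remission (protocol 3.4.2.1 and 8.2, SAP 5.5.1.3.2) carries the same condition.
- **Rescue and withdrawal.** Section 6.3 makes a change in current Crohn's treatment a treatment failure with withdrawal when worsening symptoms require it. Section 6.5 agrees: "Participants will be withdrawn from the study if they experience worsening symptoms requiring a change in their" Crohn's treatment. It adds two triggers: starting an antibiotic for gastrointestinal symptoms, and "an increase of greater than 10mg/day of prednisone or equivalent for a non-gastrointestinal condition". Withdrawal before week 6 scores as failure (8.4.2, SAP 5.5.2).
- **Stable therapy.** Section 8.1 gives as one reason for a six-week endpoint "The practical implications of not allowing changes to the medical therapy for patients with active CD for much longer than 6 weeks". Section 12.2 lists delay of a medication change as a theoretical risk of taking part. A footnote to 4.2 speaks of stable dosing for six weeks, but its asterisk sits only on the corticosteroid criterion.
- **Eligibility.** Section 4.2 excludes both starting a Crohn's drug and changing its dose. For anti-TNF agents the window is "or ustekinumab within 8 weeks prior to screening"; for other drug classes it runs from 1 to 12 weeks.

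**The concern.** The endpoint is meant to show remission achieved on a diet with background therapy held constant. For non-steroid drugs, the medication condition names only the start of a therapy. Section 4.2 treats a start and a dose change as separate events, so the endpoint's reference to initiation cannot fairly be read to include a dose change.

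The uncovered case is realistic. Everyone enters with active symptoms (sCDAI above 175) and stays under their own gastroenterologist (6.3). Biologic use is the stratification factor (3.3), so participants on biologics are expected. Escalation because symptoms persist, rather than worsen, meets no written trigger. The trial is open label, so such escalation could differ between arms. Equal leakage would dilute the difference; unequal leakage would bias it in either direction.

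The steroid wording raises a second, smaller problem. The endpoint clause sets no size limit, and it is unclear whether its reference to CD qualifies the steroid increase or only the new therapies. Section 6.5 keeps in the study a participant whose prednisone rises by 10 mg/day or less for a non-gastrointestinal condition. Two programmers could score that participant differently.

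**Working it through.** **1. Week 6 scoring, with sCDAI below 150 at the visit**

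| Event before week 6 | Endpoint clause | 6.3 / 6.5 | Scored as |
|---|---|---|---|
| New Crohn's drug started | Voids remission | Withdrawn if symptoms worsened | Failure |
| Existing non-steroid drug escalated, symptoms worse | Not named | Failure, withdrawn | Failure |
| Existing non-steroid drug escalated, symptoms not worse | Not named | Not reached | **Remission** |
| Prednisone up by 10 mg/day or less, non-gastrointestinal condition | Depends on reading | Retained | **Unclear** |

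The two extra triggers in 6.5 (antibiotic, larger steroid rise) do not touch row 3. Sections 8.1 and 12.2 express intent but attach no scoring result.

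Row 4 is harder when the steroid is given for extraintestinal Crohn's disease. Section 9.2.3 lists manifestations "such as worsening arthropathy, mouth sores, skin rashes including pyoderma gangrenosum and erythema nodosum", and the CDAI counts several as complications. Section 6.5 does not say whether such a rise is a change in Crohn's treatment (withdrawal, so failure) or treatment of a non-gastrointestinal condition (retained up to 10 mg/day).

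**2. The plan's own power figure**

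Inputs from SAP 5.2 and 5.5: 97 per arm, 40% (MSD) against 60% (SCD), two-sided 5%, chi-square test.

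Power = Φ[(d − 1.96·SE0)/SE1], with SE0 = √(2·p̄(1−p̄)/97) and SE1 = √{[p1(1−p1) + p2(1−p2)]/97}.

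With p̄ = 0.50: SE0 = √(0.50/97) = 0.0718 and SE1 = √(0.48/97) = 0.0703. Power = Φ[(0.20 − 0.1407)/0.0703] = Φ(0.843) = 80.0%. The stated 80% reproduces; nothing here disputes it.

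**3. What the gap could cost**

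One participant is 1/97 = 1.03 points of an arm's rate. The documents give no escalation rate, so assume that a fraction x of true non-remitters is escalated without worsening and scored as remission. With the same x in both arms, the observed rates are 0.40 + 0.60x and 0.60 + 0.40x, and the difference shrinks to 0.20(1 − x).

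| x (assumed) | MSD | SCD | Difference | Power |
|---|---|---|---|---|
| 0% | 40.0% | 60.0% | 20.0 | 80.0% |
| 2% | 41.2% | 60.8% | 19.6 | 78.4% |
| 5% | 43.0% | 62.0% | 19.0 | 75.9% |
| 10% | 46.0% | 64.0% | 18.0 | 71.5% |

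At x = 10% this is about 5.8 MSD participants (0.10 × 0.60 × 97) and 3.9 SCD participants (0.10 × 0.40 × 97).

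If the leak is in the MSD arm only, power at x = 2%, 5% and 10% is 74.9%, 66.1% and 49.7%. With a true rate of 40% in both arms and a leak in one arm only, the two-sided rejection rate is 5.3%, 7.1% and 13.4%. These one-arm cases are limits; nothing in the documents says the leak would be one-sided.

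**The case against.** The other side has good arguments, and they narrow the point.

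- **Most escalation is already handled.** A change required by worsening symptoms is a failure under 6.3. This stands: only escalation without worsening remains.
- **The plan intends stable therapy to week 6.** Sections 8.1 and 12.2 show this, and escalation for persistent symptoms would run against it. That makes the event less frequent, but no scoring rule follows from it. A reader might infer that 8.1 prohibits therapy changes; it only presumes that they are not allowed, in explaining the choice of six weeks.
- **Study laboratory results offer little prompt.** Calprotectin results go to sites only after all participants have finished (7.6), and study blood is drawn only at baseline, week 6 and week 12 (6.1). This largely stands, although a baseline hsCRP or a test in routine care could still prompt a change.
- **Withdrawal and scoring rules serve different purposes.** They need not share one list. This stands, so the withdrawal rules can be left alone.
- **The size is assumed.** This stands as well.

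Three stronger readings are tempting and fail. A reader might infer that 6.5 acts only on worsening symptoms; it has two other triggers, though neither reaches this case. A reader might infer that 6.5 classes Crohn's arthropathy, skin and eye disease as non-gastrointestinal; it does not classify them. A reader might assume that escalation in one arm would consume a large part of the 20-point target difference; no figure in the documents supports that.

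**Conclusion.** The gap is real and narrow. A dose or frequency increase of a non-steroid Crohn's drug already in use, made before week 6 without worsening symptoms, neither voids remission nor triggers 6.3 or 6.5. With sCDAI below 150 it is scored as remission, against the plan's own presumption of stable therapy. This is a written rule giving the wrong result in the primary endpoint of an open-label trial, and the same wording governs CDAI remission.

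Its frequency is unknown. Under an assumed equal leak of 2% to 10% of non-remitters, power falls from 80% to about 78% to 72%; unequal leakage would add bias. The plan's sample size and power figures are unaffected as calculations.

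The steroid clause is a separate ambiguity: the endpoint and 6.5 must be reconciled. The documents do not support calling it a direct contradiction.

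**What to change.** Change the scoring and leave the withdrawal rules as they are.

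1. In protocol 3.4.1.1, 3.4.2.1, 8.1 and 8.2 and SAP 5.5.1 and 5.5.1.3.2, widen the part of the clause on new therapies so that remission is voided by starting any therapy for CD or by increasing its dose or frequency, whether or not symptoms worsened. State how scheduled loading or induction doses are treated, since a footnote to 4.2 counts them as stable.
2. Derive this from the medication data taken at each visit (7.4). First confirm that the CRF records dose and interval: the SAP section 4 baseline table codes current medications only as yes or no.
3. Report the result under the definition as now written as a sensitivity analysis.
4. Reconcile the endpoint's steroid clause with the non-gastrointestinal steroid rule in 6.5, so that a retained steroid increase has one scoring result, including when it is given for extraintestinal Crohn's disease. The clinical limits are for the sponsor to set.

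The cost is wording, one derivation and possibly a CRF check or added field; 97 per arm stays. Remission rates may fall slightly in both arms, because an escalated participant who would have remitted anyway also becomes a failure.

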#### **3.4.2 Secondary Study Endpoints**

##### **3.4.2.1 Clinical Remission**

As a secondary clinical outcome, we will measure the CDAI at baseline, 6 weeks and 12 weeks. Clinical remission will be defined as a CDAI<150 in the absence of the need for increasing corticosteroid dose or initiation of new therapies for CD during the study period.

##### **3.4.2.2 Other patient reported outcome measures**

The same data elements included in the sCDAI have been combined into two item (stool frequency and abdominal pain) and three item patient reported outcome measures using the original weights derived from the full CDAI. Optimum cut-points for CDAI remission were mean daily stool frequency ≤1.5, abdominal pain ≤1, and general well-being score of ≤1 (areas under the ROC curve 0.79, 0.91 and 0.89, respectively). PRO2 and PRO3 values corresponding to CDAI scores of 150, 220, and 450 points were 8, 14, and 34 and 13, 22, and 53 respectively, and the corresponding values for CDAI changes of 50, 70, and 100 points, were 2, 5, and 8 and 5, 9, and 14, respectively. We will examine the individual components of these PROs to determine the proportion of each group that met the optimum cutpoint for remission that met the PRO2 definition of remission. Finally, we will determine the proportion of each group with a reduction in the PRO2 and PRO3 that corresponds to 100 point reduction in the CDAI.

The Patient Reported Outcome Measurement System (PROMIS) questionnaire contains several measures previously shown to correlate with disease activity and to have construct validity in CD. These include measures of fatigue, pain interference, social aspects, and sleep. See appendix H for a copy of this survey.

A subset of core variables found in the Multi-dimensional Health Assessment Questionnaire (MD-HAQ) will be used to assess physical function and joint pain, as well as RADAI Arthritis screening questions. See appendix I for a copy of these surveys

We will screen for inflammatory back pain using criteria developed by Sieper et al and assess symptom severity with the Bath AS Functional index in those who screen positive. See appendix J for a copy of these criteria.

### **3.5 Primary Safety Endpoints [If applicable]**

Not applicable.

## **4 Study Population and Duration of Participation**

### **4.1 Inclusion Criteria**

1. Age ≥18
2. Documented diagnosis of Crohn's disease
3. sCDAI score >175
4. Documentation of receipt of a baseline stool sample by the data coordinating center and hsCRP.

5. Access to a computer with internet and the ability to complete daily online surveys
6. Capable of providing consent to participate
7. Able to receive weekly food shipments delivered every Friday for 6 weeks

#### **4.2 Exclusion Criteria**

1. Pregnancy
2. sCDAI >400
3. Hospitalized patients
4. Anticipated need for surgery within 6 weeks of randomization
5. Use of the Specific Carbohydrate Diet within 4 weeks of screening
6. Start or change\*\*\* dose of thiopurines (azathioprine and 6-MP), methotrexate, natalizumab, or vedolizumab within 12 weeks prior to screening
7. Start or change\*\*\* dose of anti-TNF agents (including infliximab (Remicade), adalimumab (Humira), certolizumab pegol (Cimzia), golimumab (Simponi) or ustekinumab within 8 weeks prior to screening.
8. Start or change in dose of any 5-ASA medications within 2 weeks of screening.
9. Start or change dose of corticosteroids within 1 week of screening or a dose >20mg/day prednisone or equivalent\*
10. Use of antibiotics (other than topical formulations) for any reason within 2 weeks prior to screening
11. Known symptomatic intestinal stricture.
12. Presence of an ostomy
13. Baseline stool frequency >4 bowel movements/day when well
14. BMI <16
15. BMI ≥40
16. Celiac disease
17. Documented C difficile colitis within four weeks of screening
18. Diabetes Mellitus requiring medication
19. Albumin<2.0mg/dl, within 4 weeks of screening (if tested as part of routine clinical care)
20. Known allergy to tree nuts or peanuts
21. Other conditions that would be a contraindication to any of the study diets or preclude the participant from completing the study.
22. Currently participating in another clinical trial of a drug to treat IBD or a dietary therapy for any indication.

\*Patients may continue these medications at stable dose for the first six weeks and budesonide may be used at any dose. After the 6th week in the study, patients may taper their steroid dose. The study will provide a recommended taper schedule.

\*\*Loading/induction doses of biologic type medication will be considered a stable doses.

\*\*\*Exception for treatment failures: if a subject is determined to fail on any of the following standard lines of treatment at the treating investigator's discretion, subjects may screen for study intervention based upon the following wash out periods: 4 weeks for thiopurine and methotrexate and 8 weeks for natalizumab, vedolizumab, anti-TNF, or ustekinumab.

